## 13.6 Appendix 6: Protocol Amendment History

The document history table for this protocol and the Protocol Amendment Summary of Changes Table for the current Amendment 2 is located directly before the Protocol Synopsis.

A description of Amendment 1 is presented in this appendix.

### Amendment 1, 23 Jun 2022

#### Rationale for Amendment 1:

The main purposes of Amendment 1 are to respond to requests from regulatory authorities, to correct a typographical error in the wording of the primary safety endpoint, and to further align the trial parameters with best medical practices and previous practices in similar trials.

The summary of changes table provided here describes the important changes made in Amendment 1 relative to the original protocol, including the sections modified and the corresponding rationales. The synopsis of Amendment 1 has been modified, as needed, to correspond to changes in the body of the protocol. Minor editorial, grammatical, and formatting corrections are not included in this summary table.

Throughout the document, the protocol date and version were updated to reflect Amendment 1 and the title page was updated to reflect the protocol history.

#### Summary of Important Changes from the Original Protocol to Amendment 1:

Section Number and Name	Description of Change	Brief Rationale
Section 1.2 (Risk:Benefit Considerations) Section 6 (Study Assessments and Procedures) Section 9.3 (Participant Information and eConsent)	Added language describing increased education and guidance to participants regarding myocarditis and pericarditis	Response to FDA request for increased risk mitigation for myocarditis and pericarditis
Section 2 (Study Objectives and Endpoints)	Corrected the primary safety endpoint to read: Percentage of participants with abnormal laboratory findings drawn 8 days after study vaccination	To correct a typographical error in the number of days

Section Number and Name	Description of Change	Brief Rationale
Section 3 (Study Design) Section 13.1 (Appendix 1: Schedule of Events)	Increased the length of the screening period from 7 to 14 days, resulting in an increased study duration per participant from 187 to 194 days	To allow investigators more time to assess eligibility of participants and enhance study management
Section 3 (Study Design) Section 6.1 (Safety Assessments) Section 6.1.2 (SARS-CoV-2 Infection and COVID-19 Assessment and Definitions) Section 13.1 (Appendix 1: Schedule of Events, footnote k)	Clarified that participants will be asked to report any positive SARS-CoV-2 diagnostic test results and that investigators may verify SARS-CoV-2 infection from records of an outside medical provider	To improve surveillance for SARS-CoV-2 infections during the study and to expedite infected participant access to medical care while limiting their travel and resulting exposure to the general population while infected
Section 4.1.1 (Inclusion Criteria)	In criterion 8, increased the upper limit of body mass index from 32 to 40 kg/m 	To broaden eligibility to better reflect the target patient population without expected increased risk to participants
Section 4.1.2 (Exclusion Criteria)	In criterion 12, removed the phrase, "including a COVID-19 vaccine"	Response to Australian regulatory authority request to clarify criterion 12. The inclusion criteria and Section 5.8.2 of the protocol adequately describe the allowed intervals between COVID-19 vaccination and vaccination with IP
Section 5.2 (Study Vaccine Administration)	Inserted recommendations for needle length by sex and weight	To address revision of inclusion criterion 8, included guidance on recommended needle length
Section 5.9 (Study Holding Rules)	Timing windows for study holding rules 1c and 2a were eliminated, and a new study holding rule for myocarditis or pericarditis (1d) was established	Response to FDA request to widen the scope of study holding rules
Section 6.1 (Safety Assessments) Section 6.1.3 (Myocarditis and Pericarditis Assessment and Definitions)	Added specifications for diagnosing and evaluating cases of suspected or confirmed myocarditis or pericarditis	Response to FDA request for increased risk mitigation for myocarditis and pericarditis

Section Number and Name	Description of Change	Brief Rationale
Section 6.1.1.1.2 (Serious Adverse Events)	Clarified that all events of myocarditis and pericarditis will be considered important medical events and SAEs	Response to FDA request for increased risk mitigation for myocarditis and pericarditis
Section 6.1.1.3.2 (Reporting Suspected Unexpected Serious Adverse Reactions)	Added that cases of myocarditis or pericarditis occurring in temporal association with vaccination of study participants within 4 weeks after vaccination will be reported as SUSARs, as required by 21 CFR 312.32	Response to FDA request for increased risk mitigation for myocarditis and pericarditis
Section 6.1.3.1 (Surveillance for Asymptomatic Myocarditis and Pericarditis) Section 13.1 (Appendix 1: Schedule of Events)	Added a 12-lead ECG examination to the assessments conducted at the Day 8 visit, with cardiologist follow-up if findings of myocarditis or pericarditis are suspected or confirmed	To enhance surveillance for asymptomatic myocarditis and pericarditis and respond to FDA request for increased risk mitigation for myocarditis and pericarditis
Section 13.2 (Appendix 2: Contraceptive Guidance and Pregnancy Information)	Added tubal ligation to the list of acceptable forms of primary contraception	To provide clarity to Investigators on acceptable forms of primary contraception and to enhance study management at study sites

GMT	geometric mean titer
ICF	informed consent form
ICS	intracellular staining assay
IgG	immunoglobulin g
IP	investigational product
IMP	investigational medicinal product
LLOQ	lower limit of quantification
LNP	Lipid nanoparticles
MAAE	medically attended adverse event
MedDRA	Medical Dictionary for Regulatory Activities
mRNA	messenger ribonucleic acid
NA	not applicable
NAb	Neutralizing antibody
N protein	nucleocapsid protein
PBMC	peripheral blood mononuclear cell
PP	Per protocol
PPI	Per protocol Immunogenicity

Abbreviation	Definition
PT	Preferred Term
SAP	statistical analysis plan
RT-PCR	reverse transcription polymerase chain reaction
S protein	spike protein
SAE	serious adverse event
SARS-CoV-2	severe acute respiratory syndrome coronavirus 2
SOC	system organ class
SRT	Safety Review Team
TLF	Table, Listing and figures
Th	T helper
ULOQ	Upper limit of quantification
WHO	World Health Organization
WT	Wild type

1. Introduction

The COVID-19 pandemic caused by SARS-CoV-2 virus was declared by the WHO on 11 Mar 2020 (WHO 2020). As of 19 Jan 2022, more than 332 million cases have been reported worldwide, leading to more than 5.5 million deaths (WHO 2022). To date, there are multiple licensed or conditionally approved vaccines available that rely on a variety of vaccine technologies. All currently available vaccines are based on antigens from the original Wuhan strain (D614; wild-type, hereafter referred to as “WT”).

This is a Phase 1 FTiH study designed to evaluate the safety, reactogenicity, and immunogenicity of the GSK-CureVac CV0501 modified mRNA vaccine encoding the Omicron variant to prevent COVID-19. This study will evaluate the CV0501 vaccine as a booster vaccination in a healthy adult population of participants who have previously received at least 2 doses of an mRNA COVID-19 vaccine.

GSK and CureVac are collaborating to develop CV0501, a modified-nucleotide mRNA vaccine based on the same LNP. platform as the CVnCoV vaccine. The CV0501 mRNA encodes S protein from the Omicron variant and has been optimized to improve intracellular mRNA stability and translation for increased and extended protein expression, relative to unmodified S protein mRNA

This statistical analysis plan (SAP) was developed to provide the details of the planned statistical methodology for the analysis of both interim analyses and the preparation of the final clinical study report (CSR).

This SAP is based upon the following study documents:

- Study Protocol CV2 SARS-CV0501-012 BST (218595) Protocol Amendment 2 (26 Jul 2022)
- Participant Case Report Form (25 Jan 2023)

This SAP is to be finalized prior to first participant first visit. Major changes in the analysis that are made after database lock will be documented in the CSR along with the rationale and other details regarding the changes.

2. Objectives

2.1. Primary Objective and Endpoints

Objectives	Endpoints
Primary – Safety	
To evaluate the safety and tolerability of CV0501 at each dose level	
 Percentage of participants with each solicited local and systemic AEs during 7 days after vaccination (i.e., the day of study vaccination and 6 subsequent days (day 1 through 7) Percentage of participants with each abnormal clinical safety laboratory finding for 8 days after study vaccination Percentage of participants with unsolicited AEs for 28 days after study vaccination Percentage of participants with MAAEs, AESIs and SAEs from study vaccination through the end of the study (for 180 days after the study vaccine administration), each summarized separately

2.2. Secondary Objectives and Endpoints

Objectives	Endpoints
Secondary – Immunogenicity	
To evaluate neutralizing Ab titers against SARS-CoV-2 WT, Omicron, and Delta* variants following CV0501 booster vaccination in adult participants	
 GMTs of neutralizing Ab titers against pseudovirus bearing S protein from SARS-CoV-2 WT, Omicron, and Delta variants at each collection timepoint GMI from baseline of neutralizing Ab titers against pseudovirus bearing S protein from SARS-CoV-2 WT, Omicron, and Delta variants at each collection time point
To describe seroresponse to CV0501 based on neutralizing Ab titers against pseudoviruses bearing S protein from SARS-CoV-2 WT, Omicron, and Delta* variants	
 Seroresponse rate 28 days after the booster dose (day 29) based on neutralizing Ab titers against pseudoviruses bearing S protein from SARS-CoV-2 WT, Omicron, and Delta variants at each collection timepoint, with seroresponse defined as postboost titers $\geq 4\times$ preboost titers

CCI

3. Investigational Plan

3.1. Overall Study Design and Plan

This open-label, dose escalation first-time-in human (FtiH) Phase 1 study will evaluate the safety (including reactogenicity) and immunogenicity of a single booster dose of CV0501 vaccine in adults who have previously received at least 2 doses of an mRNA COVID-19 vaccine. Approximately 180 participants will be enrolled. The study will comprise two parts (Part A and Part B).

Part A: Participants in Cohorts 1 to 5 will be enrolled in a staggered manner to 1 of 5 cohorts with planned dose escalation of CV0501 from 12 µg up to 200 µg. Each cohort of Part A will evaluate a single dose level of CV0501 vaccine and will include 2 age groups (younger adults, ≥ 18 to < 65 years old, and older adults, ≥ 65 years old), as indicated in Table 3-1. The dose levels for the groups in Cohorts 1-3 are fixed. The dose levels for the Cohorts 4 and 5 will be as recommended by the SRT, based on their review of all available safety data and dosing scenarios.

Part B: Designed to comprise 2 single age group cohorts (≥ 18 to < 65 years old), will start based on the first interim analysis of safety and immunogenicity, provided that the SRT assesses the 12 μ g dose to be immunogenic and safe. The SRT may recommend dropping Cohorts 6 and 7 (Groups 6a and 7a) based on immunogenicity data from the groups that received the 12 μ g dose level. If the SRT determines that enrollment in Cohorts 6 and 7 may proceed, enrollment may proceed in parallel according to Table 3-2.

[figure not shown]
[figure not shown]
Table 3 1 Study Cohorts, Groups, and Study Vaccine Administration (Part A)

Cohort	Vaccine	Dose Level	Group A Younger Adults ≥ 18 to < 65 Years of Age (n range)	Group B Older Adults ≥ 65 Years of Age (n range)	Total Cohort Sample Size
1	CV0501	12 μ g	1a (min 10; max 20)	1b (min 10; max 20)	30
2		25 μ g	2a (min 10; max 20)	2b (min 10; max 20)	30
3		50 μ g	3a (min 10; max 20)	3b (min 10; max 20)	30
4		75 or 100* μ g	4a (min 10; max 20)	4b (min 10; max 20)	30
5		100,150, or 200* μ g	5a (min 10; max 20)	5b (min 10; max 20)	30

*Depending on the reactogenicity/safety findings from groups in Cohorts 1-3, the SRT may recommend 1 of 3 prespecified dosing scenarios comprising these dose levels for groups in Cohorts 4 and 5, as described in Section 3.1.1 of protocol. The dose level recommendations will be made independently for Groups A (younger participants) and B (older participants).

Table 3 2 Study Cohorts, Groups, and Study Vaccine Administration (Part B)

Cohort	Vaccine	Dose Level	Group A Younger Adults ≥ 18 to < 65 Years of Age (n range)	Total Cohort Sample Size
6	CV0501	3 μ g	6a	15
7		6 μ g	7a	15

Figure 3-1 Study Design Part A**Figure 3-2 Study Design Part B**

3.2. Study Endpoints

Please refer to Section 2.1 of this SAP.

3.3. Treatments

Investigational product (IP) in this Phase 1 study refers to the CV0501 vaccine, which is a formulation of modified mRNA encoding Omicron variant S protein microencapsulated in lipid nanoparticles (LNP) that will be administered during the study. **cci** [REDACTED]

[REDACTED]

[REDACTED]

The LNPs are composed of a

cci [REDACTED].

The following IP will be used in the study:

Intervention Name	CV0501
Type	Vaccine
Dose Formulation	Modified mRNA
Unit Dose Strength(s)	cci μg mRNA/mL
Dosage Level(s)	3, 6, 12, 25, 50, 75, 100, 150, 200 μg
Route of Administration	Intramuscular injection
Diluent	0.9% sodium chloride
Use	Experimental
IMP or NIMP	IMP
Sourcing	Provided centrally by GSK Biologicals SA or CureVac GmbH
Packaging and Labeling	IP will be provided in a glass vial as a sterile colloidal dispersion in a frozen liquid formulation as open-label supply. Each vial will be labeled as required per country requirement.

3.4. Dose Adjustment/Modifications

An overdose is any dose of study vaccine given to a participant that exceeds the planned dose for an individual within a given dose group.

There is no specific treatment recommended for an overdose. Overdose itself is not to be reported as an adverse event (AE). Overdose participants will be included in the Safety Set and excluded from Per protocol Immunogenicity (PPI) Set.

4. General Statistical Considerations

Participants will be identified in the listings by the participant identification number concatenated with the site number. Data will be displayed in all listings sorted by age group, dose group and participant number.

Continuous data will be described using descriptive statistics (n, mean, standard deviation, median, minimum, and maximum).

Categorical data will be described using the participant count and percentage for each category.

For the **summary statistics** of all numerical variables unless otherwise specified, mean, confidence interval, median, standard deviation, minimum and maximum will be displayed.

A row denoted “Missing” will be included in count tabulations where specified on the shells to account for dropouts and missing values.

There is no formal hypothesis testing in this study where statistical methods are applied, the emphasis will be on estimation with 2-sided 95% Confidence intervals (CIs).

The denominator for all percentages will be the number of participants with non-missing values of corresponding parameter in that treatment within the analysis population of interest, unless otherwise specified.

A table, figure, listing (TLF) is to be generated for any required item even where no data is available or reported. In such cases, the table, figure or listing will state: “**No Data Reported**”. This will confirm to the health authorities that all data for the tables, figures, listings, and narratives are accounted for.

Baseline will be defined as the last non-missing evaluation prior to study vaccine administration, unless otherwise specified.

Study day will be calculated as follows:

- study day prior to the injection will be calculated as: date of assessment – date of the injection
- study day on or after the date of the injection will be calculated as: date of assessment – date of the injection + 1

For Safety assessment of AEs, the intervals will be calculated as follow

- solicited AEs: the day of vaccination and 6 subsequent days (day 1 through 7)
- unsolicited AEs: the day of vaccination and 28 subsequent days (day 1 through 28)
- Medically attended adverse events (MAAEs), adverse events of special interest (AESI) and serious adverse events (SAEs): the day of vaccination and 180 subsequent days (day 1 through 180)

For calculations regarding antibody levels/titers, antibody results released as below a value will be replaced by $0.5 \times$ the value. Results released as above a value will be converted to the value. Missing results will not be imputed.

The lower limit of quantification (LLOQ) and upper limit of quantification (ULOQ) for WT NAb are the following:

LLOQ = To be defined by lab when assay calibrated.

ULOQ = To be defined by lab when assay calibrated.

calibrating conversion factor to WHO standard is 1/1.872.

NAb Result (IU/mL) = Result (NT50 titer) $\times 1/1.872$.

Details on LLOQs and ULOQs for IgG and conversion factors when available are described in Section 15.2

All safety data summaries/displays will be provided by dose group. Details will be included in the TLF shell.

All statistical analyses will be performed using SAS® software Version 9.4 or later.

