**Table 2-1 Study Objectives and Endpoints**

Primary Objectives	Primary Endpoints
To evaluate the safety and tolerability of CV0501 at each dose level	
 
Percentage of participants with each solicited local and systemic AE during 7 days after vaccination (ie, the day of study vaccination and 6 subsequent days, Days 1 through 7)
 
Percentage of participants with each abnormal clinical safety laboratory finding for 8 days after study vaccination
 
Percentage of participants with unsolicited AEs for 28 days after study vaccination
 
Percentage of participants with MAAEs, AESIs and SAEs from study vaccination through the end of the study (for 180 days after the study vaccine administration), each summarized separately
 

Secondary Objectives	Secondary Endpoints
To evaluate neutralizing Ab titers against SARS-CoV-2 WT, Omicron, and Delta variants following CV0501 booster vaccination in adult participants	
 
GMTs of neutralizing Ab against pseudovirus bearing S protein from SARS-CoV-2 WT, Omicron, and Delta variants at each collection timepoint
 
GMI from baseline of neutralizing Ab titers against pseudovirus bearing S protein from SARS-CoV-2 WT, Omicron, and Delta variants at each collection time point
 

To describe seroresponse to CV0501 based on neutralizing Ab titers against pseudoviruses bearing S protein from SARS-CoV-2 WT, Omicron, and Delta variants	
 
Seroresponse rate 28 days after the booster dose (Day 29), based on neutralizing Ab titers against pseudoviruses bearing S protein from SARS-CoV-2 WT, Omicron, and Delta variants at each collection timepoint, with seroresponse defined as postboost titers <math>\geq 4\times</math> preboost titers.
 

Tertiary Objectives	Tertiary Endpoints:
CCI	

GlaxoSmithKline Biologicals SA

CV0501 Vaccine

Protocol 218595 (CV2 SARS-COV2-012 BST) Amendment 2

26 Jul 2022

CCI

[figure not shown]

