5.1. Disposition

Participant disposition will be summarized by dose group for all participants. The number and percentage of participants for the following categories will be presented: participants who were enrolled, vaccinated, participants who discontinued from the study (i.e. did not complete the day 181 visit), participants in the Enrolled Set, PPI Set and Safety Set.

A participant may withdraw or be withdrawn from the study for any of the following reasons:

- Participant request.
- Investigator request.
- The participant is noncompliant with the protocol.
- The participant has a serious or intolerable AE(s) that, in the investigator's opinion, requires withdrawal from the study.
- The participant is lost to follow-up.

- Death.
- The sponsor terminates the study.
- The participant has safety laboratory results that reveal clinically significant hematological or biochemical changes from the baseline values, per investigator judgment
- The participant has symptoms or an intercurrent illness not consistent with the protocol requirements or that justify withdrawal
- Other reasons (e.g., pregnancy, development of contraindications of use of the IP)
- The participant withdraws consent, or the investigator or sponsor decides to discontinue their participation in the study withdrawal of consent by participant or the investigator or sponsor decides to discontinue their participation in the study

Participant status summary will also be provided which include participants who completed each visit, participants vaccinated with study vaccine, participants who had immunogenicity results at applicable visit, and participants who completed the study. Participant status summary will be also presented by dose and age group.

Participant disposition and discontinuation data will be presented in a listing sorted by age, dose group and participant number.

The number of participants included in each analysis set will be summarized. A listing of participants in each analysis set will also be provided by age, dose group and participant number. Participants excluded from the analysis sets will be listed with reason for exclusion(s) and sorted by age, dose group and participant number.

The primary reason for study discontinuation includes: Withdrawal due to AE, Lost To Follow-up, Physician Decision, Pregnancy, Site Terminated by Sponsor, Study Terminated by Sponsor, Withdrawal of Consent by Participant, Protocol Deviation, Vaccine Not Administered, Death, Other.

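### The SAP's Day 1–180 window for MAAEs, SAEs and AESIs contradicts its own wording by one day and stops short of the Day 181 end of study

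*SAP*

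**What the plan says.** SAP Section 4 (General Statistical Considerations) gives the day-numbering rule: "study day on or after the date of the injection will be calculated as: date of assessment – date of the injection + 1". Vaccination day is therefore Day 1. The same section then lists three safety windows:

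- for solicited AEs, vaccination day plus six more, ending on Day 7
- "unsolicited AEs: the day of vaccination and 28 subsequent days (day 1 through 28"
- for MAAEs, AESIs and SAEs, "the day of vaccination and 180 subsequent days (day 1 through 180"

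The Day 1–180 limit reappears in SAP 8.1.2 (primary analysis), 9.1.6 (AESIs), 9.1.7 (SAEs), 9.1.8 (MAAEs) and 9.1.11 (fatal AEs). In most of these sections it stands beside language that takes the period to the participant's exit or to the end of the study, as if the two were the same. SAP 8.1.1 sums COVID-19 adverse events that are not serious up to the end of the study and gives no day number.

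Protocol Table 2-1 defines the primary endpoint for these events as "from study vaccination through the end of the study (for 180 days after the study vaccine administration), each summarized separately". The end-of-study visit is Day 181 with a window of ±7 days (Protocol Table 13-1, SAP 15.1), and these events are collected throughout the study (Table 13-1, footnote j). SAP 5.1 ties completion to that visit: it counts "participants who discontinued from the study (i.e. did not complete the day 181 visit" as discontinued.

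**The concern.** A programmer cannot follow both halves of the Section 4 line. The words end on Day 181 and the bracket ends on Day 180. The bracket is what the table specifications repeat as an onset limit, so it is the likelier one to be coded.

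The line governs a primary endpoint in a first-in-human safety study. Coded as Day 1–180, an event that begins on the end-of-study day itself is collected but falls outside the percentage that is meant to run to the end of the study. For participants seen late in the visit window, a few further days are in doubt.

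The SAP would also treat the same late case in two ways. Virologically confirmed COVID-19 is an AESI. A non-serious case starting after Day 180 would count in the summary under 8.1.1, which has no day limit, and not in the AESI summary under 8.1.2.

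**Working it through.** **Inputs.** Study-day rule and window wording: SAP 4. End-of-study visit Day 181 ±7: Protocol Table 13-1 and SAP 15.1. Cohorts of 30 with age groups of 10 to 20: Protocol Table 3-1.

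**1. Last day of each window.** Study day = days since injection + 1.

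| Window | Days after vaccination, in words | Last day by the rule | Last day stated |
|---|---|---|---|
| Solicited AEs | 6 | 6 + 1 = 7 | 7 (agrees) |
| Unsolicited AEs | 28 | 28 + 1 = 29 | 28 (one short) |
| MAAEs, AESIs, SAEs | 180 | 180 + 1 = 181 | 180 (one short) |

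The stated Day 180 is not reproduced. The solicited-AE line is, so the rule is being read correctly. The plan's immunogenicity time points count the same way: Protocol Table 2-1 places 28 days after the booster at Day 29, and SAP 8.2.2 places 14 days after it at Day 15.

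**2. Collected days outside a Day 1–180 limit.** Days lost = max(0, exit day − 180). In-window exits run from 181 − 7 = Day 174 to 181 + 7 = Day 188.

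- Exit on Days 174–180: 0 days.
- Exit on Day 181: 1 day; 1/181 = 0.6% of follow-up.
- Exit on Day 188: 8 days; 8/188 = 4.3%.

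Under a Day 1–181 limit, an exit on Day 181 loses nothing and an exit on Day 188 loses 188 − 181 = 7 days.

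**3. Weight of one participant.** 1/30 = 3.3 percentage points in a full Part A cohort; 1/20 = 5 to 1/10 = 10 points in an age group. These figures show what one event is worth. They do not estimate the effect of the limit.

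**4. Expected effect.** The documents give no event rates. Assume a constant hazard and a 180-day participant risk p between 2% and 40%. With h = −ln(1 − p)/180 and exit on day v, the share of participants whose first event falls after Day 180 is (1 − p)(1 − exp(−h(v − 180))).

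| Everyone exits on | p = 2% | p = 40% | Expected participants of 180 |
|---|---|---|---|
| Day 181 | 0.01 points | 0.17 points | 0.02 to 0.3 |
| Day 188 | 0.09 points | 1.35 points | 0.16 to 2.4 |

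The Day 188 row is an upper limit, because it puts every participant at the far end of the visit window.

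**5. A case that splits the SAP.** A participant exits on Day 188 with non-serious, PCR-confirmed COVID-19 that began on Day 183. SAP 8.1.1 counts the case. The AESI percentage in 8.1.2 and 9.1.6, limited to Day 1–180, does not.

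**The case against.** A reader might infer that the SAP deliberately truncates follow-up, so that every participant loses up to eight days of events, which are listed but never counted. The documents do not support that, for four reasons.

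- The Section 4 words themselves run to Day 181, and 8.1.2, 9.1.6–9.1.8 and 9.1.11 also speak of the end of the study or of exit. The unsolicited-AE line has the same slip. This looks like a repeated counting error and not a choice to truncate.
- Participants who exit on Days 174–180 lose nothing.
- Days 182–188 are not clearly lost against the protocol, whose endpoint carries its own 180-day bracket. A fixed window also gives participants equal nominal follow-up despite the visit window, so following each one to actual exit is a design choice.
- For SAEs, MAAEs and deaths the SAP gives summaries and listings the same end point, while also promising listings of all SAEs and all MAAEs. Whether a late event would be listed is therefore unclear.

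All of this stands.

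One further argument is that the protocol's solicited window of 7 days after vaccination counts vaccination day as the first, so its 180 days could mean Days 1–180. That does not remove the problem. The SAP adds 180 days to the vaccination day, and the protocol endpoint also runs to the end of the study, which is Day 181.

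The study is descriptive, with no hypothesis tests, so no inference turns on the point.

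**Conclusion.** The SAP's window for MAAEs, AESIs and SAEs is wrong as written. Its words end on Day 181 and its day numbers on Day 180, and the day numbers are carried into the primary and supporting tables. Against the protocol endpoint, only Day 181 is clearly left out. Days 182–188 are left out as well only if the end of study, or exit from it, means the participant's actual last visit.

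The size is 0 to 8 days per participant, and 1 day (0.6%) at the nominal visit. Under the assumed constant hazard and 2% to 40% risk, the expected effect is 0.01 to 0.17 points if all exit on Day 181 and at most 1.35 points if all exit on Day 188. The day count follows from the SAP's formula and needs no assumption; the percentage effects do.

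The expected effect is small. The point still merits correction because it touches a primary safety endpoint, because one late SAE moves a cohort of 30 by 3.3 points, and because the SAP would count the same late COVID-19 case in one primary summary and not in another.

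**What to change.** - Choose one window for MAAEs, AESIs, SAEs and fatal AEs. At minimum use Day 1–181, which matches the protocol endpoint and the end-of-study day. The alternative is Day 1 to each participant's actual exit; the protocol's 180-day wording would then need reconciling too.
- Replace the Day 1–180 limit in SAP 4, 8.1.2, 9.1.6–9.1.8 and 9.1.11, so that words and day numbers agree.
- State that any event with onset after the chosen limit will be listed.
- Use the same end point for the COVID-19 events in 8.1.1 and the AESIs in 8.1.2, or say why they differ.
- Reconcile the unsolicited-AE line in SAP 4: 28 further days end on Day 29, whereas Day 28 needs 27. Carry the result into 8.1.1 and 9.1.5.

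The cost is SAP wording and one programming rule. No data collection changes. Only the actual-exit option also calls for a wording change in the protocol.
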